### 3.4 Sample Size

#### Lead-in phase

Approximately 30 participants will receive study intervention in the lead-in phase of the study. The example point estimates of decline rates (physical or cognitive function), and the corresponding 2-sided 95% CI (based on exact binomial distribution) are shown in Table 2. For instance, decline/worsening for TUG test is defined as an increase of at least 1 second in TUG time from baseline. The values are provided as a reference rather than a basis for decision making.

**Table 2 Estimated Decline Rates and 2-sided 95% Confidence Intervals**

Number of participants with a decline	Observed Decline Rate	95% CI		Width (%)
		Lower limit	Upper Limit	
0	0	0.00	11.57	11.57
6	20%	7.71	38.57	30.85
12	40%	22.66	59.40	36.74
18	60%	40.60	77.34	36.74
24	80%	61.43	92.29	30.85
30	100%	88.43	100.00	11.57

## Randomized phase

The sample size calculation for the randomized phase of the study is based on the primary endpoint of physical decline (using TUG test as an example). In the event that the primary endpoint or the assumed rate of decline changes based on results from the lead-in phase of the study, the sample size will be adjusted accordingly.

Approximately 120 participants in the randomized phase of the study will provide 85% power to detect a difference of 20% in the two arms using one-sided alpha of 10%. This is assuming that 20% of participants in the darolutamide arm and 40% of participants in the enzalutamide arm will have a worsening in physical function at 24 weeks as measured by the TUG test. Worsening is defined as an increase of at least 1 second in TUG time from baseline. A 10% drop-out rate is assumed.

### 4.0 Management of Analysis Data

The data from all study centers will be pooled together for analyses. Participants will not be pooled across the two phases of the study, separate analyses will be performed for the lead-in phase and randomized phase.

#### 4.1 Data Handling

Unscheduled laboratory results will not be analyzed for the visit summary of continuous values but will be included in the laboratory shift tables.

#### 4.2 Missing Data

The primary endpoint is the Proportion of patients with worsening in TUG time from Baseline. Primary endpoint-related missing data will not be imputed, but a sensitivity analysis will be conducted by replacing missing TUG times with  $\geq 1$  second increase.

All missing or partial date will be presented in the patient listings, as they are recorded on the case report form, unless otherwise specified.

A conservative approach will be taken for partial or missing dates of AE and concomitant medications. Partial dates with missing day only will be imputed to either first of month, or first dose date if it falls in the same month. Partial dates with missing month will be imputed to either

January 1 or first dose date if it falls in the same year. Completely missing dates will be imputed using first dose date, unless the end date suggests it could have started prior to this in which case the imputed date will use 1st January of the same year as the end date. In all cases, imputed start dates must be compatible with reported end dates.

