5.2 Exclusion Criteria

Participants are excluded from the study if any of the following criteria apply:

Medical Conditions

1. Symptomatic local-regional disease that requires medical intervention including moderate/severe urinary obstruction or hydronephrosis with abnormal renal function due to prostate cancer. Participants with visceral metastasis will be excluded.
2. Severe or uncontrolled concurrent disease, infection, or comorbidity
3. Past (within 6 months before the start of study intervention) or concurrent stroke, myocardial infarction, severe/unstable angina pectoris, coronary/peripheral artery bypass graft, and/or congestive heart failure (New York Heart Association Class III or IV)
4. Uncontrolled clinically significant hypertension
5. Prior malignancy. Adequately treated basal cell or squamous cell carcinoma of the skin or superficial bladder cancer that has not spread behind the connective tissue layer (i.e. pTis, pTa, and pT1) is allowed, as well as any other cancer for which treatment has been completed 3 years before the start of study intervention and from which the participant has been disease free
6. Known metastatic brain or meningeal tumors
7. Prior or concurrent central nervous system disease, such as epilepsy, Parkinson's disease, Alzheimer's disease, dementia, or multiple sclerosis
8. Active viral hepatitis, active human immunodeficiency virus (HIV), or chronic liver disease
9. Gastrointestinal disorder or procedure that is expected to interfere significantly with absorption of study treatment
10. Major surgical procedure or significant traumatic injury within 28 days before the start of study intervention

11. Seizure disorder requiring medication
12. Non-healing wound, ulcer, or bone fracture
13. Substance abuse, medical, psychological, or social conditions that may interfere with the participant's participation in the study or evaluation of the study results
14. Non-ambulatory participants who need a wheelchair. Other assistive devices (e.g., cane or walker) are permitted.
15. Any illness or medical condition that is unstable or could jeopardize the safety of the participant and his compliance in the study
16. Clinically significant limitations in cognitive function and/or physical function, such as >20 seconds in the TUG assessment

Prior/Concomitant Therapy

17. Prior treatment with any of the following:
 - Second-generation AR inhibitors, such as enzalutamide, apalutamide, or darolutamide

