9.4.2 Safety Analyses

All safety analyses will be performed on the Safety population.

Endpoints measuring physical function, cognitive function, and daily activity will also be performed on the Safety population.

Endpoint	Statistical Analysis Methods
Primary	
The primary variable in this study is the proportion of participants with a worsening in TUG time during the 24-week period from baseline. Worsening is defined as an increase of at least 1 second in TUG time from baseline by 24 weeks.
 
 At each assessment, change in TUG test time (seconds) from baseline will be calculated, and the status will be categorized as: improved, stable, or declined using the MCID of 1 second. Decline in physical function is defined as at least a 1-second increase from baseline in TUG time in each arm by 24 weeks. The proportion of participants with a decline and the 95% CIs will be summarized for each treatment arm. This rate will be compared between the two arms using Cochran-Mantel-Haenszel test adjusting for stratification factors as captured by IWRS.

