**Table 3 Study Populations for Analyses**

Population	Description
Enrolled	All participants who sign the ICF.
Full analysis set (FAS)	All enrolled participants or all randomized patients (for the randomized phase of the study). This population will be used for baseline and disposition summaries as well as for the analysis of secondary endpoints related to efficacy.
Safety population	All enrolled (or randomized for the randomized phase of the study) participants who received any quantity of study intervention, regardless of their eligibility for the study. The safety evaluation will be performed based on the study treatment actually received.  The safety population will be used for all baseline, exposure, physical function, cognitive function, daily function, and safety analyses. For the evaluation of each endpoint using an instrument or questionnaire, participants with baseline and at least one post-baseline assessment will be included.

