### 5.5.1 Primary Endpoint Analyses

The primary variable in this study is the proportion of participants with a worsening in TUG time during the 24-week period from baseline, using the best TUG time out of the measured assessments during study visits (two or

three assessments). Worsening is defined as an increase of at least 1 second in TUG time from baseline.

The proportion of participants with a worsening in TUG time and the (exact) 95% CIs will be summarized by treatment arm. A comparison between treatment arms will be made using Cochran-Mantel-Haenszel (CMH) test adjusting for Age (<75, ≥75). A sensitivity analysis will be provided by replacing missing TUG times with ≥ 1 second increase. Primary endpoint (worsening in TUG) analysis will be performed by age (<75, ≥75), metastatic state (nmCRPC, mCRPC), Pain (yes, no pain), and opioid use (yes, no opioid use). Information on pain and opioid use will be retrieved from an examination of medical history and prior medication CRFs.

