### Cognitive function

- The proportion of participants with a decline in cognitive function at 24 and within 52 weeks as assessed by HVLTR, TMT, and COWA, will be summarized. At each assessment, the change in score from baseline will be calculated and the status of cognitive function will be categorized as improved, stable, or declined using the Reliable Change Index (RCI) as shown below. Each test will be assessed individually. The proportion of participants with a decline and exact 95% CIs will be summarized. For the randomization phase, the proportion of subjects with a decline will be summarized separately by treatment arm, and a comparison between arms at week 24 and week 52 will be made using CMH test adjusting for Age (<75, ≥75).

Test	Reliable Change Index threshold (from baseline)
Hopkins Verbal Learning Test - Revised Total Recall (HVLTR TR)	±5 words HVLTR TR has a range of 0-36, recalling a list of 12 words over 3 trials.
Hopkins Verbal Learning Test - Revised Delayed Recall (HVLTR DR)	±3 words HVLTR DR has a range of 0-12.
Hopkins Verbal Learning Test - Revised Delayed Recognition (HVLTR RECOG)	±2 words HVLTR RECOG has a range of -12 to 12 words. It is equal to true positives (subject says 'yes' to 12 original words on list) minus false positives (subjects says 'yes' to distractors [12 words not on original list]).
Trail Making Test: Part A (TMTA)	±12 seconds TMT Part A is timed up to a maximum of 3 minutes. If not completed in the given amount of time, the subject is assigned a time equal to the maximum time.
Trail Making Test: Part B (TMTB)	±26 seconds

	TMT Part B is timed up to a maximum of 5 minutes. If not completed in the given amount of time, the subject is assigned a time equal to the maximum time.
Controlled Oral Word Association (COWA)	±12 words Subjects are asked to name as many words as possible all beginning with a specified letter. A total of three trials are administered, and the score on the COWA is the total number of words named across the three trials.

- The proportion of participants with a decline of >10 points from baseline in the FACT-Cog domain at 24 and within 52 weeks will be summarized in a similar fashion.

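### The primary TUG analysis has no rule for a participant who becomes physically unable to do the test, so he never counts as worsened unless a slower time was recorded earlier

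*SAP*

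**What the plan says.** SAP 5.5.1 defines the endpoint: "The primary variable in this study is the proportion of participants with a worsening in TUG time during the 24-week period from baseline". It continues: "Worsening is defined as an increase of at least 1 second in TUG time from baseline". Protocol 9.4.2 has the same definition. Both rest on a recorded time.

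Within the 24-week window the schedules (Protocol Table 1-2, SAP Table 8-2) place post-baseline TUG tests at Week 12 and Week 24 only.

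On missing data, SAP 4.2 states "Primary endpoint-related missing data will not be imputed", and the same sentence adds that "a sensitivity analysis will be conducted by replacing missing TUG times with" an increase of at least 1 second. SAP 5.5.1 repeats that sensitivity analysis. For endpoints based on an instrument, SAP Table 3 (and Protocol 9.3) limits the analysis: "participants with baseline and at least one post-baseline assessment will be included".

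Neither document says how to score a participant who attends, or is due, a TUG visit and physically cannot do the test.

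**The concern.** Loss of the ability to walk is the plainest form of the decline that the primary objective asks about, yet it leaves no TUG time and so cannot meet the definition. The resulting missing data carry information about the outcome.

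The trial is exposed to this. Metastatic disease is eligible, and the entry criteria exclude only those already in a wheelchair: "Non-ambulatory participants who need a wheelchair. Other assistive devices (e.g., cane or walker) are permitted". Falls and fractures are adverse events of interest in the protocol. Its rationale (Protocol 2.1 and 2.2) is that AR inhibitors are linked to weakness and falls, and that darolutamide, unlike enzalutamide, did not raise falls or fractures over placebo. On the trial's own hypothesis, inability could differ by arm.

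The observed worsening rate would then be too low in any arm where inability occurs, and the arm difference would be distorted if the arms differ.

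**Working it through.** **Inputs.** From SAP 3.4 and Protocol 9.2: worsening 20% (darolutamide) and 40% (enzalutamide), one-sided alpha 10%, power 85%, 120 participants, drop-out 10%. Allocation is 1:1. The share who become unable with no earlier recorded worsening, *u*, is not in the documents; every value below is an assumption.

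**Step 1: reproduce the plan's figure.** With unpooled variance, n = (1.2816 + 1.0364)² × (0.2×0.8 + 0.4×0.6) / 0.2² = 5.373 × 0.40 / 0.04 = 53.7, so 54 per arm. Then 54/0.90 = 60 per arm, or 120. With pooled variance under the null at 54 per arm, SE₀ = √(2×0.30×0.70/54) = 0.0882 and SE₁ = √((0.16+0.24)/54) = 0.0861. So z = (0.20 − 1.2816×0.0882)/0.0861 = 1.01, and power is 84.4%. The stated figure is reproduced.

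**Step 2: trace the rules.**

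| Week 12 | Week 24 | Primary analysis | Sensitivity analysis |
|---|---|---|---|
| at least 1 s slower | unable | worsened | worsened |
| stable | unable | non-worsened or missing (SAP does not say) | worsened |
| unable | unable | excluded (no post-baseline test) | not stated whether he returns |

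The second and third rows are lost from the primary analysis as worsening events.

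**Step 3: size, if the unable are part of the planned 20% and 40%.** Scored non-worsened, an arm's observed rate is p − u. Dropped, it is (p − u)/(1 − u), with 54(1 − u) analysed.

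| u, daro / enza | Scored non-worsened | Power | Dropped | Power |
|---|---|---|---|---|
| 0 / 0 | 20% vs 40% (20.0 points) | 84.4% | same | 84.4% |
| 2% / 6% | 18% vs 34% (16.0) | 73.4% | 18.4% vs 36.2% (17.8) | 77.9% |
| 3% / 8% | 17% vs 32% (15.0) | 70.5% | 17.5% vs 34.8% (17.3) | 76.3% |
| 4% / 10% | 16% vs 30% (14.0) | 67.5% | 16.7% vs 33.3% (16.7) | 74.6% |

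As another scenario, let the same share of worsened participants be unable in both arms. At 10% and 25%, power is 80.0% and 72.4% if they are scored non-worsened, and 82.2% and 78.0% if dropped.

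**Step 4: direction.** Scored non-worsened, the difference changes by u(daro) − u(enza).
- Enzalutamide only, 5%: 20% vs 35%, 15 points.
- Darolutamide only, 5%: 15% vs 40%, 25 points.
- Equal, 3% each: 17% vs 37%, still 20 points, with both rates too low.

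If the unable are dropped, each arm's rate falls by u(1 − p)/(1 − u), about 0.8u on darolutamide and 0.6u on enzalutamide. The difference then shrinks only when inability on enzalutamide exceeds that on darolutamide by about a third or more.

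**Step 5: the planned sensitivity analysis.** Assume 10% missing per arm, unrelated to function. All counted as worsened, the rates are 0.9×20% + 10% = 28% and 0.9×40% + 10% = 46%. The difference is 18 points and power at 60 per arm is 78.1%. Ordinary missed visits dilute this analysis, so it does not isolate inability.

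**The case against.** The strongest reply is that the SAP does have a pre-specified analysis in which missing tests count as worsened. That is true, and the gap is confined to the primary analysis. It does not close the gap, for the reasons in Steps 2 and 5.

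Other points that stand:
- The planning rates are described as worsening measured by the TUG. If 20% and 40% already exclude the unable, subtracting them again double-counts, and the power losses in Step 3 do not arise.
- Entry requires KPS of at least 80 and life expectancy of at least 1 year, and excludes TUG above 20 seconds, so inability may be rare. Cane and walker users are eligible, so needing a device need not mean a missing test.
- Falls, fractures and KPS deterioration are summarized separately. Such decline would be visible elsewhere in the report, though not in the primary result.
- The endpoint and sample size are to be reassessed after the lead-in phase. That makes a change easy but does not supply the rule.

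A reader might infer from the Trail Making Test rule, "If not completed in the given amount of time, the subject is assigned a time equal to the maximum time", that the SAP already treats this situation for another instrument. It does not. That rule caps a test that was attempted; it does not cover a participant who cannot take it.

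**Conclusion.** The point holds for the primary analysis. Followed as written, the plan never counts as worsened a participant who becomes physically unable to do the TUG by Week 24 and has no earlier recorded increase of at least 1 second. Worsening is understated in any arm where this happens.

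The size is unknown. Under the assumed 2-4% and 6-10%, taken as part of the planned rates and scored non-worsened, the difference is 14-16 points and power 68-73% instead of about 84%. If dropped, it is 16.7-17.8 points and 75-78%. If inability is rare and equal between arms, the effect is small.

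Four stronger readings are tempting but not supported:
- That all severe decline is lost. A participant already 1 second slower at Week 12 is still counted.
- That the SAP scores a stable Week 12 with a missing Week 24 as non-worsened. This is an inference from the no-imputation and inclusion rules; he could equally be treated as missing. Neither reading counts him as worsened.
- That the bias always runs toward no difference. It widens the difference if inability is commoner on darolutamide.
- That the trial is shown to be underpowered. The power figures are scenarios.

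**What to change.** In SAP 4.2 and 5.5.1 and Protocol 9.4.2, count as worsened a participant who attends or is due a TUG visit up to Week 24 (Week 52 for that endpoint) and cannot do the test because of physical inability, for example fracture, or being wheelchair- or bed-bound. Apply the same rule to time to worsening. Let a visit with recorded inability satisfy the post-baseline requirement in SAP Table 3 and Protocol 9.3; otherwise those unable from Week 12 stay excluded.

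Record the reason for each missing TUG on the CRF, if it is not already captured (the CRF is not among the documents). Do not let hospitalization alone qualify, because an unrelated admission is not functional decline. For tests missing for other reasons, state whether a stable Week 12 result stands as non-worsened or the participant is missing.

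Keep the present no-imputation rule and the all-missing-as-worsened analysis as sensitivity analyses, and say whether the latter includes participants with no post-baseline test.

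The cost is one reason code and a few sentences. The downside is some site judgement about the reason in an open-label trial, which a restricted list limits. The reassessment before randomization is the natural time to make the change.

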### 4.3 Coding Conventions for Events and Medications

Event/Medication	Coding/Mapping Convention
AE, Medical History Coding	MedDRA version 23.0 or higher
Lab Test Grade	NCI CTCAE version 5.0
Prior and Concomitant Medications	WHO DDE version 2020Mar or higher

AE = adverse event; CTCAE = Common Terminology Criteria for Adverse Events; MedDRA = Medical Dictionary for Regulatory Activities; NCI = National Cancer Institute; WHO-DDE = World Health Organisation Drug Dictionary Enhanced.

## 5.0 Statistical Methods

### 5.1 General

Demographic and baseline characteristics, efficacy assessments, and safety data will be summarized for the lead-in Phase and for the Randomization Phase separately. The Lead-in Phase summary will be based on a single group of subjects treated with darolutamide, while the Randomization Phase will be summarized by darolutamide, enzalutamide and overall groups. Unless otherwise stated, all analyses described below will be applied to both phases of the trial.

All variables will be analyzed with appropriate statistical methods. Continuous data will be presented as n, mean, standard deviation, median, quartiles, minimum, and maximum. Continuous variables will be described by absolute value and as change from baseline per analysis time point. Categorical data will be presented as frequency counts, percentages and 95% CI. All raw data collected will be listed.

#### 5.1.1 Definitions

**Baseline:** The last measurements taken prior to first exposure to study drug, including Day 1 measurements taken pre-dosing. If patients have no value as defined above for a particular parameter, the baseline value will be missing.

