- g BFI is a 5 minute self-assessment tool that identifies fatigue in cancer participants over a 24-hour period.
- h The first TUG assessment is to be performed before the first dose (either during screening or Week 1 Day 1).
- i Once the baseline procedures are completed, the first administration of study intervention will be provided at the study center and the participant will be provided with additional medication to take as scheduled through the Week 4 visit. (Each participant will be instructed to bring any remaining drug back to the center at the Week 4 visit.)
- j At this and each subsequent visit, the participant will return dispensed but unused study intervention to the investigator for recording on the CRF. Reasons for non-compliance will be recorded. A new supply of study drug sufficient to meet the dosing requirements of each participant will be dispensed.
- k Participants remaining on treatment beyond Week 52 will continue, where possible, to receive study intervention and assessments until the final evaluation of the randomized phase (i.e. at Week 52 for the last participant, see Section 4.4.1).
- l Prior to the final evaluation of the randomized phase of the study, all participants will go into Week 53 active follow-up or survival follow-up as applicable.
- m Each participant should complete an end of treatment visit after discontinuation of study intervention for any reason. All anti-cancer treatments after discontinuation of study intervention in this study will be recorded on the CRF at the end of treatment visit. See Section 4.4.2 for more details once the date of the final evaluation of the randomized phase is determined.
- n Survival will be followed with contact with the participant and/or his caregiver every 3 months following the date of last treatment until the end of the study for participants treated with darolutamide (see Section 4.4.2).

Table 1–2 Schedule of Activities for the Randomized Phase (darolutamide, enzalutamide)													
Assessment	Screening	Randomization	Intervention + Observation Period									End of treatment visit (30 days after last dose) ⁿ	Survival follow-up ^{m,o}
			Week 1 Day 1 ⁱ	Week 4 ^k	Week 8	Week 12	Week 24	Week 38	Week 52	from Week 53: Active follow up every 3 months ^{l,m}			
Time window allowed	within 21 days prior to randomization		within 21 days after randomization	± 7 days	± 7 days	± 7 days	± 7 days	± 14 days	± 7 days	± 1 month	+ 1 month	± 1 month	

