Treatment dispensing / accountability			X	←=====→									
AE review ^b			←=====→										
AEs of interest review, including fall ^c			←=====→										
Timed Up and Go assessment (TUG) ^d	X ^h		X ^h			X	X		X	X			
Short Physical Performance Battery (SPPB) ^d			X			X	X		X	X			
Accelerometry assessment ^e	X					X	X		X	X			
Cognitive function ^f			X				X		X	X			
Brief Fatigue Inventory (BFI) ^g			X	X	X	X	X		X				
Patient Health Questionnaire (PHQ-9)			X	X	X	X	X		X	X			
Survival status												X	

X = measure/action to be performed at the time point indicated

←=====→ = measure/action to be performed continually during the time period indicated

AE = adverse event; BFI = Brief Fatigue Inventory; COWA = Controlled Oral Word Association; CRF = case report form; HVLTR = Hopkins Verbal Learning Test - Revised; PHQ-9 = Patient health questionnaire-9; PSA = prostate-specific antigen; SPPB = Short Physical Performance Battery; TMT = Trail Making Test; TUG = Timed Up and Go

- a PSA will be assessed at the same time as other laboratory assessments. A time window of ± 14 days is allowed for laboratory and PSA assessments.
- b Including survival, pain, radiographic progression, metastases, and skeletal events
- c AEs of interest are fractures, falls, and hypothyroidism
- d Physical function tests include SPPB and the TUG assessment.
- e Accelerometry assessment will require the participant to wear an accelerometry device on the wrist or hip for a minimum of 7 days at each time point. The first accelerometry assessment is to be performed before the first dose (i.e. during screening).
- f Cognitive function tests include the HVLTR, TMT, and COWA, as well as the patient-reported outcome questionnaire FACT-Cog.
- g BFI is a 5 minute self-assessment tool that identifies fatigue in cancer participants over a 24-hour period.
- h The first TUG assessment is to be performed before the first dose (either during screening or Week 1 Day 1).
- i Once the baseline procedures are completed, the first administration of study intervention will be provided at the study center and the participant will be provided with additional medication to take as scheduled through the Week 4 visit. (Each participant will be instructed to bring any remaining drug back to the center at the Week 4 visit.)

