- j Laboratory and PSA analyses and the physical examination will need to be repeated if they are not within 21 days from randomization. Week 1 Day 1 cannot be longer than 3 weeks from randomization.
- k At this and each subsequent visit, the participant will return dispensed but unused study intervention to the investigator for recording on the CRF. Reasons for non-compliance will be recorded. A new supply of study drug sufficient to meet the dosing requirements of each participant will be dispensed.
- l Participants remaining on treatment beyond Week 52 will continue, where possible, to receive study intervention and assessments until the final evaluation of the randomized phase (i.e. at Week 52 for the last participant, see Section 4.4.1).
- m Prior to the final evaluation of the randomized phase of the study, all participants will go into Week 53 active follow-up or survival follow-up as applicable.
- n Each participant should complete an end of treatment visit after discontinuation of study intervention for any reason. All anti-cancer treatments after discontinuation study intervention in this study will be recorded on the CRF at the end of treatment visit. See Section 4.4.2 for more details once the date of the final evaluation of the randomized phase is determined.
- o Survival will be followed with contact with the participant and/or his caregiver every 3 months following the date of last treatment until the end of the study for participants treated with darolutamide, and until the final evaluation of the randomized phase for participants treated with enzalutamide (see Section 4.4.2).

2. Introduction

Prostate cancer is the second most common cancer and the fifth leading cause of cancer death among men worldwide ([World Health Organization 2017](#)). It is the most common non-cutaneous cancer and the second leading cause of cancer-related deaths in men in Europe ([World Health Organization 2008](#)) and the United States (USA) ([Hirsch et al. 2001](#)). The most significant morbidity of prostate cancer is bone metastases.

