4.1.1 Randomization

This is an open-label study; however, the specific intervention to be taken by a participant will be assigned using an IWRS. The site will need to access the IWRS prior to the start of study intervention administration for each participant. The site will record the intervention assignment on the applicable case report form (CRF), if required. Randomization will be stratified by age (<75, ≥75 years).

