6.1 Study Intervention(s) Administered

Intervention Name	Darolutamide	Enzalutamide
Type	drug	drug
Dose formulation	film-coated tablet	soft tablet
Unit dose strengths	300 mg	40 mg
Dosage Level	600 mg twice daily	160 mg once daily
Route of administration	oral	oral
investigational medicinal product (IMP) / non- investigational medicinal product (NIMP)	IMP	IMP
Sourcing	Provided centrally by the sponsor	Commercially available
Packaging and Labeling	Will be provided in white opaque wide-necked high density polyethylene (HDPE) bottles closed with white opaque screw cap polypropylene (PP) / PP with seal polyethylene child-resistant. Each container will be labeled as required per country requirement.	Will be supplied via prescription for those in the enzalutamide arm as commercially available from the pharmacy and will not be supplied by the sponsor.
Current/Former Name(s) or Alias(es)	Darolutamide (BAY 1841788 / ODM-201)	Enzalutamide (Xtandi®)

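### In the randomised phase, the SPPB, cognitive, BFI and PHQ-9 baselines, and TUG if it is done or repeated on Day 1, can be recorded after open-label allocation is known

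*SAP*

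**What the plan says.** Protocol Table 1-2 and SAP Table 8-2 have separate columns for Screening, Randomization and Week 1 Day 1. The row "Short Physical Performance Battery (SPPB) ^d" is blank under the first two and first marked at Week 1 Day 1. The same is true of "Cognitive function ^f" (HVLT-R, TMT, COWA and FACT-Cog), BFI and PHQ-9.

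The window for Week 1 Day 1 is "within 21 days after randomization", and footnote j repeats the limit: "Week 1 Day 1 cannot be longer than 3 weeks from randomization".

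TUG is marked at both Screening and Week 1 Day 1, and footnote h accepts either for the first test. Accelerometry is fixed at screening (footnote e).

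SAP 5.1.1 sets baseline for all parameters as "The last measurements taken prior to first exposure to study drug, including Day 1 measurements taken pre-dosing". The anchor is first dose, not randomisation.

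On allocation, Protocol 4.1.1 states: "This is an open-label study; however, the specific intervention to be taken by a participant will be assigned using an IWRS". SAP 3.2 says blinding techniques are not needed. Protocol Table 8-1 asks for independent blinded assessors for TUG where possible. There is no such provision for SPPB or the cognitive tests.

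**The concern.** Randomisation balances only what is fixed before it. A baseline measured after allocation, by someone who may know the arm, is no longer a pure covariate: it can itself respond to the assignment. That matters here for two reasons.

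- The measures depend on effort (TUG, SPPB, cognitive tests) or self-report (BFI, PHQ-9, FACT-Cog).
- The endpoints are proportions crossing a small threshold relative to baseline: 1 second for TUG, 1 point for SPPB in the SAP (0.5 in the protocol), and 1 point for BFI and PHQ-9. A small baseline shift can move a participant across the line.

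The primary CMH test adjusts only for age group, so nothing in the analysis would absorb such a shift. For SPPB, cognition, BFI and PHQ-9 there is no scheduled pre-allocation value to fall back on.

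**Working it through.** **1. Timing of each baseline in the randomised phase**

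| Instrument | Marked pre-dose at | Baseline under SAP 5.1.1 | Relative to allocation |
|---|---|---|---|
| SPPB | Day 1 only | Day 1 | 0 to 21 days after |
| HVLT-R, TMT, COWA, FACT-Cog | Day 1 only | Day 1 | 0 to 21 days after |
| BFI, PHQ-9 | Day 1 only | Day 1 | 0 to 21 days after |
| TUG | Screening or Day 1 | Latest pre-dose value | Before, unless done or repeated on Day 1 |
| KPS | Screening and Day 1 | Day 1 | 0 to 21 days after |
| Accelerometry | Screening | Screening | Before |

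**2. Can the arm be known by then?** The site contacts the IWRS before treatment starts (Protocol 6.3). Footnote i requires baseline procedures to precede the first dose. No section requires them to precede allocation or its disclosure. Protocol 6.1 says of enzalutamide: "Will be supplied via prescription for those in the enzalutamide arm as commercially available from the pharmacy". A participant who has filled that prescription before Day 1 would know his arm.

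**3. The plan's own figure.** Inputs from Protocol 9.2: 20% vs 40%, one-sided alpha 10%, power 85%, drop-out 10%. With unpooled variance, n per arm = (1.2816 + 1.0364)² × (0.2×0.8 + 0.4×0.6) / 0.20² = 53.7, so 54. Then 2 × 54 = 108 evaluable, and 108 / 0.90 = 120. This reproduces the plan. (Power at 54 per arm with the pooled-variance test is 84.4%.) The calculation has no term for baseline timing, so moving the baseline leaves N unchanged.

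**4. Sensitivity range.** The documents give no SD for TUG change and no size of bias, so both are assumed. Further assumptions: no true difference, 20% worsening in both arms, normal changes, 54 per arm, and recorded baseline shifted by d seconds in the enzalutamide arm only. Positive d means a faster recorded baseline.

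- Mean change: μ = 1 − SD × 0.8416. For SD 1.5 s, μ = −0.262.
- Apparent enzalutamide worsening: p₁ = 1 − Φ((1 − μ − d)/SD). For d = 0.25, p₁ = 1 − Φ(1.0124/1.5) = 25.0%.
- Chance of a one-sided result favouring darolutamide: Φ((p₁ − 0.20 − 1.2816 × SE₀)/SE₁). SE₀ uses the pooled proportion and SE₁ the separate ones. For d = 0.25, SE₀ = 0.0804 and SE₁ = 0.0802, giving Φ(−0.662) = 25.4%.

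| d (s), SD 1.5 s | p₁ | Error rate (nominal 10%) |
|---|---|---|
| +0.10 | 21.9% | 15.0% |
| +0.25 | 25.0% | 25.4% |
| +0.50 | 30.6% | 49.2% |
| −0.25 | 15.7% | 3.1% |

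For d = +0.25 the error rate is 36.6% with SD 1 s and 16.5% with SD 3 s. The last row of the table shows that the opposite sign makes the test conservative. These figures show how sensitive a 1-second threshold is. They do not estimate what would happen in this trial.

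**The case against.** The other side has several fair points.

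- **TUG.** Exclusion 16 gives TUG over 20 seconds as an example of a disqualifying limitation, and Protocol 8 requires screening evaluations to be completed to confirm eligibility. A pre-randomisation TUG is therefore implied for many men, and footnote h does not clearly require a repeat. This stands: the primary-endpoint part is conditional. Blinded TUG raters, where achieved, reduce the rater risk but not the participant's own knowledge.
- **Length of gap.** Twenty-one days is a maximum, and Day 1 may be the day of randomisation. This stands, but same-day testing can still follow the IWRS call.
- **Supply.** A reader might infer from the different supply routes that the gap between allocation and baseline is longer in the enzalutamide arm. The documents do not show this: both arms share the same 21-day limit.
- **Cancellation.** If knowing the arm shifts answers at baseline and equally at later visits, part of the shift cancels in the change score, whereas with a pre-randomisation baseline it would not. That is possible, and open-label follow-up remains a limitation either way. It does not justify a baseline measured after allocation, because the cancellation cannot be verified.
- **Rationale for last pre-dose.** Several exclusions run to the start of study intervention, and BFI covers only 24 hours, so closeness to dosing has value. This supports testing close to randomisation, not after it.
- **Timing of the decision.** The randomised phase is conditional on the lead-in, and its design and endpoints are still to be settled. This lowers the urgency but not the need.

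**Conclusion.** The point holds as an opportunity for bias. For SPPB, the cognitive tests with FACT-Cog, BFI and PHQ-9, following the plan as written yields baselines taken 0 to 21 days after open-label allocation. For TUG it holds only where a Day 1 test is done, in which case the SAP rule uses that value even if a screening TUG exists.

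A reader might go further and conclude that the primary result will be biased, or biased towards darolutamide. The documents do not support that. They give no size and no direction, and the error rates in the working rest entirely on an assumed SD and an assumed one-arm shift. The single-arm lead-in is not affected.

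This should be fixed but is not a bar to proceeding: the change is cheap, and most of the affected endpoints are secondary.

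**What to change.** Make the change when the randomised phase is finalised.

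- **Schedule (Protocol Table 1-2, SAP Table 8-2).** Place baseline TUG, SPPB, cognitive tests, BFI and PHQ-9 after consent and before the site accesses the IWRS. They can be done at the existing screening visit or on the randomisation day before the IWRS call, as close to randomisation as practical.
- **SAP 5.1.1.** For the randomised phase, define baseline for these instruments as the last value before randomisation. Apply the same rule to KPS, which is judgment-based, already measured at screening, and has its own deterioration endpoint.
- **Sensitivity analysis.** Repeat the analysis with the last pre-dose value where a Day 1 value exists.
- **Unchanged.** Keep the last pre-dose value for laboratory tests, PSA and vital signs.

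Sample size and power do not change. The costs are testing some men who are then not randomised, and an older baseline: up to 21 days before first dose if done on the randomisation day, or up to about 21 + 21 = 42 days if done at the start of screening. The Randomization column currently carries no assessments, so sites choosing that day would need to plan for the battery then.
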